14. FINANCE AND INSURANCE	
15. CONFLICTS OF INTEREST	
16. REFERENCES	
APPENDICES	

LIST OF ABBREVIATIONS

ADE	Adverse Device Effect
AE	Adverse Event
AxMP	Auxiliary Medicinal Product
DMC	Data Monitoring Committee
eCRF	electronic Case Report Form
FAPD	Functional abdominal pain disorder
FGID	Functional gastrointestinal disorder
GCP	Good Clinical Practice
GP	General Practitioner
IBS	Irritable Bowel Syndrome
ICH	International Conference of Harmonisation
ISRCTN	International Standard Randomised Controlled Trial Number
NHS	National Health Service
NICE	The National Institute for Health and Care Excellence
PedsQL-3.0-GIS	The Paediatric Quality of Life Inventory™ Gastrointestinal Symptoms Module
PI	Principal Investigator
REC	Research Ethics Committee
SADE	Serious Adverse Device Effect
SAE	Serious Adverse Event
TMG	Trial Management Group
TSC	Trial Steering Committee
UADE	Unanticipated Adverse Device Effect

TRIAL SUMMARY

Title:	Randomised, placebo-controlled multi-centre study to assess the safety and efficacy of Ent erosgel® in the treatment o f functional abdominal p ain in c hildren and young people		
Acronym:	ENTOPIC		
Phase:	Medical device study for CE marking purposes		
Chief Investigator:	[name]		
Sponsor:	Enteromed Ltd		
Intervention:	Enterosgel® (Bioline Products s.r.o), which is an intestinal adsorbent categorised as a class IIa medical device		
Study Design:	UK two-centre, parallel arm, randomised, double-blind, placebo-controlled trial to evaluate the efficacy, tolerability and safety of Enterosgel® in the treatment of functional abdominal pain in children and young people age 3-18 years. After an initial 2-week observation phase eligible patients will be randomised 1:1 to receive Enterosgel® or placebo for 4 weeks during the double-blind treatment phase, then all patients will receive open-label Enterosgel® treatment for a further 4 weeks. All children will have the option to increase the dose of the intervention if required to control their symptoms during both phases. The patients then return to standard care.		
	remote recruitment appointment, a two-week initial observation period (weeks 1-2), a follow-up remote appointment at Baseline week 3 to confirm eligibility and a call at week 4 to check compliance, and follow-up remote appointments at weeks 6 and 10. Patients or carers will complete a daily study diary during 10 weeks (2 weeks of observation and 8 weeks of intervention). In addition, children and parents/carers complete questionnaires (PedsQL 3.0 GIS module, KIDSCREEN-27) at baseline and 6- and 10-weeks.		
Objectives:	Primary objective		
	The primary objective of this study is to test the efficacy (superiority) of Enterosgel® (Bioline Products s.r.o, Czech Republic) compared with placebo in terms of change in mean abdominal pain score as recorded in the daily diary between the initial observation phase (weeks 1-2) and the double-blind treatment phase (weeks 3-6).		
	Secondary objectives		
	The secondary objectives for the double-blind treatment phase are:		
	 To determine the efficacy of Enterosgel[®] compared with a parallel placebo group in terms of: 		
	 abdominal pain as recorded in the daily diary 		
	change in stomach pain and other gastrointestinal symptoms		
	2. To determine effects of treatment on health-related quality of life		
	related to treatment		
	The secondary objectives for the open-label treatment phase are:		
	 In patients who had received placebo as blinded treatment, to compare the study outcome measures (same as for double-blind phase above) over the open-label Enterosgel treatment period to the preceding placebo treatment period. 		
	 In patients who had received Enterosgel[®] as the blinded treatment, to test whether the treatment benefits (in terms of study outcome measures; same as for double-blind phase above) can be effectively maintained with Enterosgel[®]. 		

	 To evaluate safety of Enterosgel[®] through reported adverse events potentially related to treatment.

	 Average number of stools per week <3 Previous use of Enterosgel® Use of antidepressant agents, unless used at a stable dose for at least 6 weeks Use of any probiotic supplements, other intestinal adsorbents, slow-release medications or strong opioids Participation in any research where treatment is provided in the last three months Pregnancy or not willing to use contraception for the duration of the study in females of childbearing potential defined as any female over 11 years of age and who has not undergone surgical sterilization (hysterectomy or bilateral conhorectomy) or is not postmenopausal
Study schedule:	Screening appointment in person/video conference (0 weeks) • Patient screening • Confirming eligibility • Informed consent • Demographic information • Medical history and concomitant medications • Provide information about the study Recruitment call – remote (0 weeks)
	 Informed consent Questionnaires (PedsQL 3.0 GIS module, KIDSCREEN-27) Initial observation period (weeks 1-2) Daily symptom diary (continue for 10 weeks) Baseline (remote): Start of double-blind phase (beginning of week 3) Review of changes in medical history and concomitant medications Instruction on use of study intervention Randomisation Double-blind study treatment received by post Follow-up call – remote (week 3)
	 Ensure participant continuing in the study and discuss any potential issues Adverse events Follow-up 1 appointment – remote (end of week 6) Questionnaires (PedsQL 3.0 GIS module, KIDSCREEN-27) Review of changes in medical history and concomitant medications Record Adverse Events Adequate relief question Check compliance and advise on any issues Open label study treatment received by post Follow-up 2 appointment – remote (end of week 10) Questionnaires (PedsQL 3.0 GIS module, KIDSCREEN-27) Review of changes in medical history and concomitant medications Record Adverse Events Adequate relief question Check if any arrangements for clinical follow-up as part of routine care

1. BACKGROUND

1.1 FUNCTIONAL ABDOMINAL PAIN

Functional abdominal pain disorders (FAPDs), also known as disorders of gut-brain interaction, are estimated to affect 13.5% of children worldwide and 10.5% of European children [1]. They can result in a decreased health related quality of life (HR-QOL) across all factors (emotional, social and physical) [2], school absenteeism and reduced participation in school and after-school activities similar to children with inflammatory bowel disease [3] and have significant health care costs [4]. A recent audit of children attending Alder Hey Gastroenterology Outpatients, showed 23.2% fulfilled the Rome IV criteria [5] for a functional gastrointestinal disorder (FGID). Amongst these children 75.5% had a FAPD (H2), of those 42.9% had irritable bowel syndrome (IBS; H2b); 14.3% functional dyspepsia (H2a); 4.8% functional abdominal pain not otherwise specified (H2d); and 1.6% abdominal migraine (H2c). Furthermore, it is estimated that up to 25% of childhood FGIDs continue into adulthood [6].

Clinical practice highlights the limited treatment options. A recent systematic review and meta-analysis of 91 studies (7226 children) evaluated dietary treatments (n=730), pharmacological treatments (n=2140), probiotic treatments (n=1762), and psychosocial treatments (n=2952) [7]. The study concluded only two treatments with moderate certainty were probably more effective for treatment success than control treatments. These included hypnotherapy and cognitive behavioural therapy, all other treatments were either not effective or the data were of very low certainty. For example, amitriptyline resulted in significant improvement in children in India, but this was an open-label trial and there was a trend to more frequent adverse events in the treatment arm [8]. A small study of melatonin in children with FAPDs also treated with a probiotic showed an initial, modest improvement in abdominal pain but this was not sustained [9]. Another small study of gut-directed hypnotherapy showed decreased pain frequency and intensity in children with functional abdominal pain and IBS but no improvement in quality of life (QOL) or school absence [10]. A recent study of Mebeverine in adolescents showed it was ineffective in the treatment of IBS and functional abdominal pain not otherwise specified [11]. In summary, there is an absence of safe, effective and evidence-based treatments for FAPDs in children.

1.2 INTESTINAL ADSORBENTS IN THE TREATMENT OF FAPDs

Enterosgel® is an oral intestinal adsorbent that binds bacterial toxins, viruses, immune chemicals and bile acids in the gut [12,13]. The active component is polymethylsiloxane polyhydrate. It is classified as a medical device class IIA as it is excreted unchanged being neither absorbed nor metabolised [12]. Enterosgel® is free from preservatives, sugar and other additives and considered to be non-allergenic. It is available over the counter as a gel in a tube or sachet. The gel is taken diluted in water and has no taste. The European database of suspected adverse drug reaction reports no adverse reactions in Europe since it was certified in 2008 (http://www.adrreports.eu/en/index.html). It is certified for the treatment of acute diarrhoea and IBS with diarrhoea (IBS-D) for all ages.

Enterosgel® improves stool frequency and consistency in adults [14] and children with diarrhoea [15-18]. A recent UK randomised, placebo-controlled trial evaluated Enterosgel® in 440 adults with IBS-D (age 16-75yrs) recruited from primary and secondary care, and a virtual site [19]. The primary outcome (percentage of responders for abdominal pain and stool consistency score) was higher in the Enterosgel® (37.4%) than the placebo group (24.3%; NNT:8; odds ratio 1.95 [1.28 to 2.99, p=0.0020]). Statistically significant benefits in the Enterosgel® arm were also found for diary-based outcomes of stool consistency/frequency, pain, bloating and urgency. Questionnaire scores showed significant differences for the IBS Severity Scoring System and IBS-QOL questionnaires. Following an open-label phase, 75.9% of patients reported adequate relief of symptoms.

In IBS, Enterosgel® is thought to target several factors including immune proteins, bacterial breakdown products and bile acids and normalise the intestinal microflora [19]. Based on its mechanisms of action and the encouraging findings in adult IBS-D, Enterosgel® could be a safe and effective treatment for childhood FAPDs.

This trial will be the first placebo-controlled randomised trial with Enterosgel® in children and young people with FAPDs.

2. AIMS AND OBJECTIVES

2.1 AIMS

The aims of this study are:

- 1. To determine the efficacy of Enterosgel® treatment for 4 weeks in improving FAPD symptoms in children with Functional dyspepsia [H2a], IBS [H2b]; Abdominal migraine [H2c] or Functional abdominal pain not otherwise specified [H2d])
- 2. To determine the safety and tolerability of Enterosgel® for the treatment of FAPDs
- 3. Document the effects of treatment up to 8 weeks on symptoms
- 4. To determine the efficacy in sub-group analysis of children with specific FAPDs.
- 5. To obtain data to power a larger follow-on study to determine the clinical and cost effectiveness of Enterosgel® for the treatment of FAPDs in children.

2.2 OBJECTIVES

2.2.1 Primary objective

The primary objective of this study is to test the efficacy (superiority) of Enterosgel® (Bioline Products s.r.o, Czech Republic) compared with placebo in terms of change in mean abdominal pain score as recorded in the daily diary between the initial observation phase (weeks 1-2) and the double-blind treatment phase (weeks 3-6).

2.2.2 Secondary objectives

The secondary objectives for the **double-blind treatment phase** (weeks 3-6) are:

- 1. To determine the efficacy of Enterosgel® compared with a parallel placebo group in terms of:
 - abdominal pain as recorded in the daily diary
 - change in stomach pain and other gastrointestinal symptoms
- 2. To determine effects of treatment on health-related quality of life
- 3. To evaluate safety of Enterosgel® through reported adverse events potentially related to treatment

The secondary objectives for the open-label treatment phase (weeks 7-10) are:

- 4. In patients who had received placebo as blinded treatment, to compare the study outcome measures (same as for double-blind phase above) over the open-label Enterosgel® treatment period to the preceding placebo treatment period.
- 5. In patients who had received Enterosgel® as the blinded treatment, to test whether the treatment benefits (in terms of study outcome measures; same as for double-blind phase above) can be effectively maintained with Enterosgel®.
- 6. To evaluate safety of Enterosgel® through reported adverse events potentially related to treatment.

3. STUDY DESIGN AND OUTCOME MEASURES

3.1 STUDY DESIGN

This is a UK two-centre, parallel arm, randomised, double-blind, placebo-controlled trial to evaluate the efficacy, tolerability and safety of a medical device, Enterosgel®, in the treatment of functional abdominal pain in children and young people. (**Figure 1**).

Children aged 3-18 years will be recruited over a 12-month period by review of NHS referrals to general paediatric and paediatric gastroenterology clinics at Alder Hey Children's NHS Foundation Trust, and Bristol Royal Hospital for Children and by review of children previously diagnosed with a FAPD. All children will be reviewed by an experienced paediatrician. A thorough clinical assessment including any appropriate investigations (e.g. gastro-intestinal endoscopy; abdominal ultrasound, faecal calprotectin) will be performed with careful attention to potential alarm features in children with chronic abdominal pain to ensure that other diagnoses are excluded [20]:

- Family history of inflammatory bowel disease, celiac disease, or peptic ulcer disease
- Persistent right upper or right lower quadrant pain
- Dysphagia
- Odynophagia
- Persistent vomiting
- Gastrointestinal blood loss
- Nocturnal diarrhoea
- Arthritis
- Perirectal disease
- Involuntary weight loss
- Deceleration of linear growth
- Delayed puberty
- Unexplained fever

Children will only be recruited once a diagnosis of an FAPD has been confirmed according to Rome IV criteria [21] and including the following syndromes:

- H2a. Functional Dyspepsia
- H2b. Irritable bowel syndrome
- H2c. Abdominal Migraine
- H2d. Functional Abdominal Pain Not Otherwise Specified

The study involves a screening clinic appointment (routine clinical care; week 0) and remote recruitment appointment, a two-week initial observation period (weeks 1-2), a follow-up remote appointment at Baseline week 3 to confirm eligibility and a call at week 4 to check compliance, and follow-up remote appointments at weeks 6 and 10. The daily on-line diary will be completed for 10 weeks (Wong-Baker FACES Pain Rating Scale) and questionnaires (PedsQL 3.0 GIS module, KIDSCREEN-27) at screening, 6 and 10 weeks. No further clinic visits or blood, stool or other samples are required for research purposes.

The screening clinic appointment will take place within a routine clinic visit which may be on site or remote. Recruitment during a remote clinic call will only occur where the child has already been clinically assessed and examined by the referring paediatrician. Children previously diagnosed with a FAPD can be considered for invitation to join the study without the need for an additional routine clinic visit. Patients and their parent/carer that have a clinician's confirmed diagnosis with specific FAPD category (H2a, H2b, H2c or H2d) and deemed eligible to join the study will receive patient information sheets and a pregnancy test kit for those eligible. After 24 hours consideration the Research Nurse will call and book a remote recruitment

appointment or an additional clinic visit. The research nurse will recruit and consent patients during the recruitment appointment for a 2week observational phase.

Eligible patients at baseline will be randomised 1:1 to receive Enterosgel® or placebo for 4 weeks during the double-blind treatment phase (weeks 3-6), then all patients will receive open-label Enterosgel® treatment for a further 4 weeks (weeks 7-10). Patients will take a dose in the morning and evening, with an increase in dose from 53% to 80% of the recommended daily dose for diarrhoea at week 3-4 (including in the placebo arm). The purpose of the dose adjustment is two-fold; first, it will maximise the efficacy of the active treatment by making a step-wise increase in dose and second, it will provide us with data to help define the optimal dosage regimen(s) for Enterosgel®.

After the double-blind treatment phase, all patients will receive open-label Enterosgel® treatment for 4 weeks. As in the double-blind phase, patients will take an increase in dose from 53% to 80% of the recommended daily dose for diarrhoea at week 3-4. As the treatment will be open-label, this is a pragmatic part of the trial, allowing us to better understand the optimal dosage regimen(s) for Enterosgel®. After 4 weeks of open-label treatment, the patients will return to standard care.

The study outcomes align with the 8 core outcome set for FAPDs in children as outlined by articles listed on the COMET Core Outcome Measures in Effectiveness Trials database [22].

The initial study design and patient facing documents have been reviewed by the Generation R Liverpool Young Person's Advisory Group, which comment and advise on paediatric trials. The group consists of children and parents and they will continue to be consulted on all aspects of the trial development and delivery and be represented on the Trial Management Group.

Figure 1. Study design.

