5. INTERVENTIONS AND STUDY DEVICE

5.1 INTERVENTION

5.1.1 Treatment allocation

5.1.1.1 Double-blind phase

For the double-blind treatment phase, patients will be randomised in 1:1 ratio using a computer-based randomisation tool (Sealed Envelope Ltd, UK) to:

Control Group: will receive placebo daily for 4 weeks

Interventional Group: will receive Enterosgel® daily for 4 weeks

Randomisation will be based on the minimisation method where treatment allocation will be stratified by study centre, sex and age group (15-18 years; 7-14 years and 3-6 years). Minimisation allocates subjects to the treatment group that best maintains balance in stratifying factors. It is effective even at small sample sizes and with multiple stratification variables [24].

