5.1.4 Treatment dosage

5.1.4.1 Double-blind phase

Both the placebo and Enterosgel® will be provided in 90g tubes, each containing a single dose of treatment (age 7-18 years) or half a dose of treatment (age 3-6 years). Each Enterosgel® tube contains either 8, 12 or 18g of Enterosgel® (Bioline Products s.r.o, Czech Republic) pre-diluted in 65-80ml of potable water. Each placebo tube contains 90ml of potable water.

The age-related treatment dose per day is one dose in the morning 1 hour before or after a meal, and one dose in the evening 1 hour before or after a meal. The daily dose for week 1-2 will be 53% of the recommended age-related daily treatment dose for acute diarrhoea, the dose will increase at week 3-4 to 80% of the dose for acute diarrhoea.

Study-specific age-related dosage instructions for the double-blind treatment period are provided in **APPENDIX C: TREATMENT USE INSTRUCTIONS (DOUBLE-BLIND PHASE)**.

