5.1.4.2 Open-label phase

For the open-label treatment phase, all patients will receive Enterosgel® in 225g tubes with the appropriate age-related measuring spoon (5g, 10g or 15g). The age-related dosage morning and evening and the stepwise dose increase at week 3-4 will align with the double-blind phase. Study-specific dosage instructions are provided in Error! Reference source not found.

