8. STATISTICS

8.1 SAMPLE SIZE CALCULATION

In a previous clinical trial of Mebeverine in the treatment of FAPD in children [30], the mean (SD) change from baseline in the Wong-Baker FACES Pain Rating Scale in the placebo arm was -1.2 (1.5). We consider that a 1-point larger reduction in the Enterosgel arm (a mean change from baseline of -2.2) would be clinically significant. The number of patients required to observe this difference with 80% power and α =0.05 is approximately n=130 (or n=65 per arm). We would increase the sample size to n=154 (77 per arm) to allow for 15% drop-outs.

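### Section 3.1 says the dose step will help define the optimal dosage, but a fixed, unrandomised step cannot separate dose from time on active treatment without strong assumptions

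*Protocol*

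**What the plan says.** Section 3.1 gives the step-up two purposes. The first is to maximise efficacy. The second is that "it will provide us with data to help define the optimal dosage regimen(s) for Enterosgel". For the open-label phase the same section describes a pragmatic part of the trial, "allowing us to better understand the optimal dosage regimen(s) for Enterosgel".

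The schedule is fixed in the body of the protocol:

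- Section 3.1 describes dosing "with an increase in dose from 53% to 80% of the recommended daily dose for diarrhoea at week 3-4 (including in the placebo arm".
- Section 5.1.4.1 sets the lower level for treatment weeks 1-2 and then states that "the dose will increase at week 3-4 to 80% of the dose for acute diarrhoea".
- Section 5.1.4.2 carries this over: "The age-related dosage morning and evening and the stepwise dose increase at week 3-4 will align with the double-blind phase".
- Appendices C and D, shown for ages 7-14, give the same two blocks of two weeks.

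What is randomised is the arm only. In section 5.1.1.1, "patients will be randomised in 1:1 ratio using a computer-based randomisation tool" to placebo or Enterosgel.

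The Trial Summary says something different: "All children will have the option to increase the dose of the intervention if required to control their symptoms during both phases".

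**The concern.** A trial can inform the choice between two dose levels if some children receive one level while comparable children receive the other at the same stage of treatment. Here no group stays at the lower level, starts at the higher level or steps up at another time. A better result in the second fortnight could come from the higher dose, from two more weeks of active treatment, or from both.

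Within an arm, and throughout the open-label phase, the change is also open to placebo response and regression to the mean, because there is no concurrent placebo after week 6.

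At stake is what may be concluded about dosage. The question whether Enterosgel, given as this stepped regimen, beats placebo is not touched.

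**Working it through.** The protocol gives no figure for this claim, so there is none to reproduce. The check is whether the planned schedule can identify an 80% versus 53% contrast at all.

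**Inputs.** The schedule is taken from sections 3.1, 5.1.4.1 and 5.1.4.2. The step at week 3-4 is read as treatment weeks, as in section 5.1.4.1 and Appendix C, so it falls in study weeks 5-6 and again in 9-10.

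| Study weeks | Enterosgel arm | Placebo arm |
|---|---|---|
| 1-2 | no treatment | no treatment |
| 3-4 | 53%, 1st fortnight on active | placebo |
| 5-6 | 80%, 2nd fortnight | placebo |
| 7-8 | 53%, 3rd fortnight | 53%, 1st fortnight |
| 9-10 | 80%, 4th fortnight | 80%, 2nd fortnight |

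The two arms are never on 53% and 80% in the same calendar period.

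**Model.** Mean pain in a cell = period effect (common to both arms) + dose effect (a53 or a80) + time-on-active effect (c2, c3, c4 for the 2nd, 3rd and 4th fortnight; the 1st is the reference). Write D for the Enterosgel arm minus the placebo arm. Period effects cancel in D:

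- D(3-4) = a53
- D(5-6) = a80 + c2
- D(7-8) = (a53 + c3) − a53 = c3
- D(9-10) = (a80 + c4) − (a80 + c2) = c4 − c2

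**Double-blind phase alone.** Parameters: 3 periods + a53 + a80 + c2 = 6. Rank: 5. The change between blocks is

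D(5-6) − D(3-4) = (a80 − a53) + c2.

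Only this sum is estimable. The dose contrast is recovered only if c2 = 0, that is, if two more weeks on treatment make no difference (5 parameters, rank 5).

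**Both phases, unrestricted time effect.** Parameters: 5 + 2 + 3 = 10. Rank: 9. The 80% level is given only in a 2nd or 4th fortnight on treatment, so its column in the design matrix equals the sum of those two time columns. The contrast is not estimable.

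**Both phases, linear time effect.** Put c2 = b, c3 = 2b, c4 = 3b. Then D(7-8) = D(9-10) = 2b, and for example

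a80 − a53 = D(5-6) − D(3-4) − D(7-8)/2.

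Parameters 8, rank 8: estimable. This uses the return to 53% at week 7 and the delayed start in the placebo arm. It also assumes no carry-over from the 80% block into weeks 7-8.

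**The same, allowing the open-label switch to act differently in the two arms (effect s).** Now D(7-8) = D(9-10) = 2b + s, so b and s cannot be told apart. Parameters 9, rank 8: not estimable. Such an effect is plausible. At week 7 the blind ends, the presentation changes from pre-diluted tubes to gel measured by spoon (sections 5.1.2.2 and 5.1.4.2), and only one arm is taking the active product for the first time.

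These are ranks of the table of cell means, so a larger sample does not change them.

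**If the Trial Summary applied instead.** An increase taken when symptoms require it makes dose a consequence of the outcome. Children at the higher level would differ from the rest by their response so far, and the dosage claim would still be unsupported. The instruction in Appendices C and D to stop, and then to resume once daily after two days without stool, likewise produces dose variation driven by an outcome.

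**The case against.** Four counter-arguments deserve weight.

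1. *The placebo arm steps up too, concurrently and blinded.* This stands. Placebo response, regression to the mean and calendar time are removed from the between-arm difference in weeks 3-6. What remains is time on active treatment, and that alone is enough to block the dose contrast.
2. *The design is not devoid of dose information.* This stands in part. A reader might infer that dose and time are wholly confounded. That goes too far, since the week-7 return to 53% and the delayed-start arm identify the contrast under the linear model above. That is identification by assumption, not by design.
3. *The wording is only rationale.* This stands, and it limits the severity. The text speaks of helping to define and of understanding better. The aims, objectives and outcomes (sections 2 and 3.2) and the analyses in section 8.2 contain no dose comparison. A reader might infer that the sponsor plans to credit a better second fortnight to the higher step, or to carry it into product instructions. The protocol says neither.
4. *Open-label data can still inform a regimen.* This stands for tolerability and acceptability. The diary in Appendix A records daily how many drinks were taken and whether constipation was the reason for taking none.

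A reader might also infer a size for the problem from section 8.1, where the cited placebo change of −1.2 exceeds the 1-point benefit sought. The documents do not support this. A change common to both arms cancels in the between-arm difference. For within-arm changes, the protocol does not say how a fall of that kind is spread over the four weeks.

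**Conclusion.** The point holds and is minor. The two statements in section 3.1 give the step-up a property that the design lacks: the data describe a stepped regimen and do not identify the effect of dose. No analysis plan can change that without assuming either no effect of time on treatment or, using both phases, a linear duration effect, no carry-over and no arm-specific effect of the open-label switch.

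No magnitude in pain-score points can be given, because the documents hold no information on the effect of time on active treatment. The conclusion rests on the fixed schedule in sections 3.1, 5.1.4.1 and 5.1.4.2. The Trial Summary contradicts that schedule. The claim fails on either version, though for a different reason.

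A reader might take this as a weakness of the main result. It is not. The primary outcome averages weeks 3-6 and compares the whole stepped regimen with placebo as randomised.

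**What to change.** - Reword the two optimal-dosage statements in section 3.1 to say that the data describe the stepped regimen and do not identify the effect of dose.
- Report the Enterosgel-placebo difference in mean diary pain with its 95% CI separately for study weeks 3-4 and 5-6, labelled as descriptive, and state that a difference between the blocks cannot be attributed to dose.
- Limit open-label dose information to descriptive tolerability and acceptability.
- Reconcile the Trial Summary (optional increase for symptoms) with sections 3.1, 5.1.4.1 and 5.1.4.2 (fixed step for all). Which version is right is for the sponsor and investigators to say.

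The cost is a few sentences and one table from the daily diary that is already collected. The sponsor gives up a claim that the design cannot support. No change to the dosing is proposed.
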